TITLE Assessment of the Impact of a Personalised Nutrition Intervention in Impaired Glucose Regulation

DESIGN Pilot Study;

Allocation: RCT

Intervention model: Parallel assignment with an active control

Masking: None

Primary purpose: Prevention

AIMS • To compare the impact of a DNA-based diet on glucose regulation in prediabetic individuals with that of standard care.

OUTCOME MEASURES Primary outcome (measured at 6 weeks):

- Difference in 0 minutes glucose on 75g oral glucose tolerance test between the control arm and the intervention arm.

Secondary outcomes:

- Cross-arm and within arm differences (compared to 0 week measurements) between the control arm, intervention arm, and the exploratory arm, in respect of:
 - 120 minutes glucose on 75g oral glucose tolerance test
 - 0 minutes glucose on 75g oral glucose tolerance test
 - HbA1c
 - Weight
 - BMI
 - Lean mass
 - Fat mass
 - Waist circumference
 - Total cholesterol
 - Fasting Triglycerides
 - LDL cholesterol
 - HDL cholesterol
 - HOMA Insulin sensitivity and secretion measurement
 - 120 minute c-peptide following 75g oral glucose tolerance test
 - Systolic blood pressure
 - Diastolic blood pressure
 - Food frequency (by food frequency questionnaire (FFQ) and 24hour recall)
 - Energy intake
 - Carbohydrate intake

- Fat intake
- Saturated fat intake
- Salt intake
- Vitamin D
- Vitamin B6
- Vitamin B12

All of the above secondary outcomes will be measured at 6 and 12 weeks, and a follow-up at 26 weeks (with the exception of HbA1c which will only be measured at 12 and 26 weeks).

- The number of participant withdrawals during the trial.

POPULATION Adults with impaired glucose regulation defined by impaired fasting glucose (IFG) or impaired glucose tolerance (IGT) in line with WHO criteria (N = 180).

ELIGIBILITY Inclusion criteria:

- Adults over 18 years of age
- Impaired glucose regulation including IFG and IGT by fasting glucose, OGTT or HbA1c criteria
- Access to smartphone with an operating system of iOS 8.0 or above, or Android 4.0 or above.

Exclusion criteria:

- Diabetes
- Pregnant or planning pregnancy
- Breastfeeding
- Enrolled in other clinical trials
- Have active malignancy or under investigation for malignancy
- Severe visual impairment
- Reduced manual dexterity
- Use of psychiatric, anti-diabetic, and/or weight loss medication, and/or oral steroids
- Bariatric surgery
- History of illnesses that could interfere with the interpretation of the study results (e.g. HIV, Cushing syndrome, chronic kidney disease, chronic liver disease, hyperthyroidism, hereditary fructose intolerance, alcohol or substance abuse)
- Unable to participate due to other factors, as assessed by the Chief Investigator

STUDY DURATION 1 year 11 months

PARTICIPANT DURATION 6 months

NUMBER OF SITES 1

SCHEMATIC OF STUDY DESIGN

[figure not shown]

Figure 1: Study design. The asterisk indicates the start of the intervention period.

1 INTRODUCTION

1.1 BACKGROUND

Diabetes is amongst the most common long term conditions, with the number of people affected worldwide quadrupling from 108 million in 1980 to 422 million in 2014 (Mathers & Loncar 2006). Its prevalence in people over 18 years of age has risen from 4.7% in 1980 to a staggering 8.5% in 2014 (Mathers & Loncar 2006). In 2012, there were 1.5 million deaths as a direct result of diabetes, making it the 8th leading cause of death amongst both sexes, and the 5th leading cause of death amongst women. There were a further 2.2 million deaths as a result of complications due to higher-than-optimal glucose levels (WHO 2016). In 2013, 6% of the UK adult population (2.7 million people) were diabetic (Gatineau et al. 2014), 90% of whom had type 2 diabetes (UK 2014). A further 5 million people were estimated to be at high risk of developing type 2 diabetes (NHS n.d.). This has led to a cost of £8 billion per year to the NHS, 80% of which is due to diabetes-related complications such as cardiovascular disease, amputations, renal failure and sight loss (Hex et al. 2012).

The potential for lifestyle interventions to reduce the progression to type 2 diabetes from high risk states has been demonstrated in a number of randomised control trials (RCTs) in different countries, with a meta-analysis of RCTs suggesting that lifestyle intervention in high risk subjects can halve the incidence of diabetes (Neil Thomas et al. 2010). The lifestyle modification RCTs that show reduced progression to diabetes in high risk subjects have given impressive results (Diabetes Prevention Program Research Group 2002; Pan et al. 1997; Kosaka et al. 2005; Tuomilehto et al. 2001; Ramachandran et al. 2006). However, they have been expensive and labour intensive, with multiple personal contacts (including in some instances home visits) for those in the trial who were deemed to be failing to achieve their goals (Diabetes Prevention Program Research Group 2002). Such intensive input is not practical on a large scale. Alternative methods to induce behavioural change, including contact via mobile phones or home computer, have been employed with success in other clinical situations (Ramachandran et al. 2013) .

Furthermore, the use of dietary interventions to adjust postprandial glucose levels have indicated the potential benefits of an individualised approach. Traditional approaches of predicting postprandial glucose level such as carbohydrate intake or glycemic index (American Diabetes Association 2015; Bao et al. 2011), have shown mixed results. Carbohydrate intake has been shown to be a poor predictor of postprandial glucose levels (Conn & Newburgh 1936; Zeevi et al. 2015). In fact, individual responses to carbohydrate intake were sufficiently disparate to distinguish two groups of carbohydrate-sensitive and carbohydrate-insensitive individuals, emphasising the need for an individualised intervention (Zeevi et al. 2015). Using the glycemic index of food succumbs to the caveats of examining only a single macronutrient profile, and neglecting the wide range of food combinations at a given meal, and the proximity of the next/previous meal

and/or physical exercise (Dodd et al. 2011). The importance of an individualised approach is most clearly illustrated by the discrepancy in postprandial glucose readings between people who consume identical meals (Vrolix & Mensink 2010; Vega-López et al. 2007; Zeevi et al. 2015), highlighting the need for a personalised treatment plan.

Personalised nutrition enables health interventions by optimising multiple dietary components simultaneously and enhancing motivation to adhere to dietary advice. An innovative approach to personalised nutrition has emerged in the form of DNA-based dietary advice. This intervention provides people with dietary advice that has been tailored to information based on their DNA. In a study in which a DNA-based diet was used to treat obesity, the DNA-based diet had a dramatic effect on the fasting blood glucose levels of participants (Arkadianos et al. 2007). 57% of the intervention group ($n = 30$, receiving DNA-based recommendations), achieved fasting blood glucose values $<5.6\text{mmol/L}$ (100mg/dL), compared to 25% of the control group ($n = 16$), 90 days following treatment ($OR = 1.98$). Notably, the DNA-based nutritional advice was not tailored to be a weight loss program, or indeed to improve prediabetic biomarkers. It was targeted to optimise the nutrient profile of a given individual. Another point of interest was the longevity of the effect. The greatest difference between the intervention and control group was found >300 days post treatment; the control cohort showed a slight increase in BMI, compared to the decrease found in the intervention group. This may indicate that there is a greater probability of long-term adherence to nutritional guidelines when tailored, actionable DNA-based advice is provided. A prospective study examined the potential for DNA-based advice to enhance adherence to nutrition protocols (Nielsen & El-Sohemy 2012). Participants received general dietary advice, versus the same advice supplemented with information based on their DNA ($n = 149$). Those in the intervention group reported a greater understanding of the dietary advice (93% versus 78%), they were more likely view the advice as useful (88% versus 72%), and they were more interested in receiving further recommendations (95% versus 76%).

1.2 RATIONALE

The standard treatment protocol for pre-diabetic individuals in the UK is a brief consultation with their clinician highlighting the dangers of an increased risk of diabetes, and some general information regarding healthy eating and the benefits of regular physical activity. The individual will subsequently be contacted every 3 years to assess the state of their glucose regulation (NICE 2012). Despite the implementation of this system, incidence rates of diabetes have continued to rise over the years. From 1994-2011, the number of women diagnosed with diabetes has risen from 1.9 – 4.9%, and 2.9 – 7.0% for men (England 2016). In response to this, the NHS launched the NHS Diabetes Prevention Program (DPP) in 2016. The aforementioned studies and the predictions of the DPP are in agreement that an intensive lifestyle intervention can radically reduce incidence rates of diabetes. However, these interventions are costly, labour-intensive and require the health system to

pre-identify prediabetic patients. The last point is one of the greatest challenges to any diabetes prevention program, as many at-risk individuals will not self-assess to pre-empt a glucose regulation test (Christensen et al. 2004). Our solution aims to assess the improvement in glucose regulation by following a DNA-based diet in comparison with the standard protocol. Furthermore, our intervention will assess whether a positive change can be implemented by using an app to aid in grocery shopping for a DNA-based diet. If effective, this solution could provide a costeffective, widely-distributed, easily scalable prevention tool for improving glucose regulation in high risk individuals. Moreover, the non-invasive nature of the intervention, paired with the autonomy that it provides the individual in choosing their food choices, enables it to be a lowrisk intervention. Furthermore, as a DNA-based diet is relevant for the general public, it has the potential to perform the preventative measures on individuals who do not self-identify as pre-diabetic.

In this pilot study, we propose to use genetic data to guide personalised nutrition in people with impaired glucose tolerance to demonstrate the impact of personalised nutrition on glucose metabolism, anthropometry, non-glucose metabolism and quality of life.

2 OBJECTIVES

2.1 PRIMARY OBJECTIVE

- To compare differences in the impact of a DNA-based diet and standard care in improving glucose regulation in pre-diabetic individuals

2.2 SECONDARY OBJECTIVES

- To assess the ability of a DNA-based diet to improve the macro- and micro-nutrient profile of pre-diabetic participants.
- To assess the impact of a DNA-based diet on clinical markers including cholesterol, body composition and blood pressure, as they relate to diabetes risk.
- Where applicable, to assess changes in anthropometric measurements as a result of following a DNA-based diet, where they relate to diabetic risk reduction.

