3.5 STUDY OUTCOME MEASURES

Primary outcome: Difference in 0 minutes glucose on 75g oral glucose tolerance test between the control arm and intervention arm at 6 weeks

Secondary outcomes: 120 minutes glucose on 75g oral glucose tolerance test
0 minutes glucose on 75g oral glucose tolerance test
HbA1c
Weight
BMI
Lean mass
Fat mass
Waist circumference
Total cholesterol
Fasting Triglycerides
LDL cholesterol
HDL cholesterol
HOMA Insulin sensitivity and secretion measurement
120 minute c-peptide following 75g oral glucose tolerance test
Systolic blood pressure
Diastolic blood pressure
Food frequency (by food frequency questionnaire and interviews) Energy intake
Carbohydrate intake
Fat intake
Saturated fat intake
Salt intake
Vitamin D
Vitamin B6
Vitamin B12

All secondary outcomes will be measured at 6, 12 and 26 weeks (with the exception of HbA1c which will only be measured at 12 and 26 weeks).

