For each of the primary and secondary outcomes, formal statistical analysis will be based on appropriate linear models. From each linear model, an estimate of the magnitude of the treatment effect i.e. the difference in mean outcomes between the control arm and intervention arm, will be derived, together with adjusted (least squares) means, 95% confidence intervals, and associated p-values. Initial exploratory analyses of these models will include relevant baseline covariates, including baseline values of the endpoint, and

all covariates that are statistically significant will be retained in the model for the purposes of deriving the final treatment effect outcomes. Baseline values of the endpoint will be retained in each model regardless of statistical significance.

All analyses will be conducted using two-sided tests and at a significance level of 5%.

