## 1.9 Analyses of quantitative data

Continuous outcomes will be compared between groups using the modified analysis of covariance (ANCOVA). This approach has been chosen because it is more powerful than other alternatives such as t-test.

A linear regression model will be used to analyse the association between post-intervention values of the outcomes with intervention arm adjusting for their baseline value, participant age and sex.

Let  $y_{it}$  denote the outcome value for individual  $i$  at time  $t$ ,  $x_i$  her covariates (e.g. sex, age) and  $d_i$  her intervention arm. The ANCOVA model is given by:

$$y_{it} = \beta_0 + \beta_1 y_{i0} + \beta_2 x_i + \gamma d_i + \varepsilon_{it}$$

An extension of the basic ANCOVA model will consider an interaction between the intervention indicator and the baseline values to test the assumption that the treatment effect varies with baseline status.

In addition, changes in continuous outcomes from baseline will be analysed using a linear regression model of the difference between the outcome value at visit and its baseline value. Using the same notation, the change model is

$$\Delta y_{it} = y_{it} - y_{i0} = \beta_0 + \beta_1 x_i + \gamma d_i + \varepsilon_{it}$$

Covariates will be centered in the analyses. Robust linear regression *lmrob* from the R package *robustbase* will be used for the ANCOVA analysis unless specified otherwise. It uses the MM-estimator to estimate the regression coefficient accounting for departure from normality of the outcomes.

Assessment of models' goodness of fit will include careful examination of residuals using graphical methods (scatter plot, boxplot and QQ plot) and detection of outliers. In addition, equality of the post-treatment variances will be tested using Levene's test.

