### **1.19 Variables related to nutrition**

- Dietary intakes

- Derivation: dietary intakes (Total energy, carbohydrate, fat, saturated fat, salt and vitamin B6, B12, D) will be assessed using 24-hours recall questionnaire (food frequency questionnaire [FFQ]) at visits 4, 5, 7, 9 and 11. The FETA software will be used to derive average daily nutrition contents from the FFQ data. In addition, 25-hydroxyvitamin D and vitamin B6 will be measured directly by the Pathology Department in Hammersmith Hospital (Imperial College Healthcare NHS Trust).
- Analysis: the analysis will be conducted separately for each nutrient using modified ANCOVA and LMM as described above;
- Additional analysis: additional dietary intakes may be examined.

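### The objective is the nutrient profile, but self-reported nutrients are analysed only as absolute daily amounts, so a single nutrient test cannot separate quantity from composition

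*Protocol*

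**What the plan says.** Protocol 2.2 and SAP 1.2 both state the objective as "To assess the ability of a DNA-based diet to improve the macro- and micro-nutrient profile of pre-diabetic participants". Neither document defines a profile or says what would count as improving it. Protocol 1.1 describes the DNA-based advice in an earlier obesity study as aimed at each person's nutrient profile and not at weight loss, so composition is at least part of the intended mechanism.

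The outcomes in Protocol 3.5 and SAP 1.5 are energy and single nutrients, for example "Saturated fat intake". SAP 1.19 lists the self-reported intakes as "Total energy, carbohydrate, fat, saturated fat, salt and vitamin B6, B12, D" and gives their scale: "The FETA software will be used to derive average daily nutrition contents from the FFQ data". On the analysis it says that "the analysis will be conducted separately for each nutrient using modified ANCOVA and LMM as described above". The model in SAP 1.9 compares arms "adjusting for their baseline value, participant age and sex", with no energy term. Protocol 9.4 allows more covariates, but only baseline ones: "Initial exploratory analyses of these models will include relevant baseline covariates". Follow-up energy therefore never enters a nutrient analysis, either as a divisor or as a covariate.

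Some dietary measures are not daily amounts. SAP 1.19 adds that "25-hydroxyvitamin D and vitamin B6 will be measured directly by the Pathology Department in Hammersmith Hospital". Protocol 3.5 lists food frequency, and Protocol 9.4 plans polytomous regression of dietary habits. SAP 1.19 also allows further intakes to be examined, without naming any. Neither document has a percent-of-energy, per-1000-kcal or energy-adjusted outcome, and protein is not listed.

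**The concern.** A profile is most naturally read as composition: how intake is divided among nutrients. A daily amount mixes composition with total food eaten and total food reported. Masking is none (Protocol summary; SAP 1.4), intake is self-reported, and each nutrient is tested at 5% with no multiplicity adjustment (SAP 1.20).

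Two things are at stake for objective 2.2. First, a general difference between arms in quantity or reporting appears as lower fat, saturated fat and salt, and no single test can show that composition stayed the same. Second, people differ widely in total energy. That spread enters every absolute amount as noise, so a true shift in macronutrient composition is harder to detect than it need be.

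**Working it through.** **The plan's own figure.** There is none to reproduce. The sample size (50 per group, raised to 60; Protocol 9.3) is for fasting glucose, and no intake SD, correlation or power is given anywhere.

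**Inputs from the documents.** Two-sided 5% (Protocol 9.4); baseline-adjusted ANCOVA (SAP 1.9); 50 evaluable or 60 randomised per arm (Protocol 9.3).

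**Assumed inputs.** Mean energy 2000 kcal; energy CV c = 20-35%; fat share 35% of energy with SD 5 points, so d = 5/35 = 0.143; visit-to-visit correlation 0.6 for energy and 0.5 for share; 9 kcal per gram of fat.

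**Step 1: what one test can see.** Fat in grams = energy × share / 9, on average 2000 × 0.35 / 9 = 77.8 g. Multiply one arm's energy by 0.9 at the same share, or its share by 0.9 at the same energy: grams fall by 10% either way. The share falls only in the second case.

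**Step 2: standard errors, as a fraction of the mean** (c = 0.28, 50 per arm).
- Grams: CV² = c² + d² + c²d² = 0.0784 + 0.0204 + 0.0016 = 0.1004, so CV = 0.317.
- Correlation of grams between visits: (0.6 × 0.0784 + 0.5 × 0.0204 + 0.3 × 0.0016) / 0.1004 = 0.575.
- SE(grams) = 0.317 × √(1 − 0.575²) × √(2/50) = 5.2%.
- SE(share) = 0.143 × √(1 − 0.5²) × √(2/50) = 2.5%, or 0.87 points.

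**Step 3: rejection probability** ≈ Φ(|effect| / SE − 1.96).
- Uniform 10% fall, grams: 10/5.19 = 1.93, giving 0.49. At c = 0.20 (SE 4.09%) it is 0.69, and at c = 0.35 (SE 6.21%) 0.36. For % of energy the effect is zero, so 0.05.
- True shift of 2.5 points at equal energy, or 2.5/35 = 7.14% of the mean. Grams: 7.14/5.19 = 1.38, giving 0.28. Share: 7.14/2.47 = 2.89, giving 0.82.

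Simulation with log-normal energy agrees:

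| Scenario (fat) | n per arm | Grams | % of energy |
|---|---|---|---|
| Uniform 10% fall, CV 20-35% | 50 | 39-73% | 4-5% |
| Uniform 10% fall, CV 28% | 60 | 59% | 5% |
| True 2.5-point shift, CV 20-35% | 50 | 22-40% | about 81% |
| True 2.5-point shift, CV 28% | 60 | 34% | 87% |
| True 2.5-point shift, CV 28%, share SD 7 points | 50 | 24% | 53% |

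**Step 4: other nutrients, under a log-scale model.** Assumed log-SD of energy 0.3, correlation 0.5, 60 per arm. For a uniform 10% fall, absolute tests reject in 0.52 (carbohydrate), 0.49 (fat), 0.45 (saturated fat) and 0.39 (salt) of trials, and at least one of the four rejects in 0.69. The energy-relative tests reject about 0.05 to 0.06 each, and at least one in 0.21. Over the wider range of assumed SDs and correlations (energy log-SD 0.2-0.4, density log-SD 0.10-0.25, correlation 0.4-0.7), a single absolute test rejects in 0.27-0.95. For a nutrient with wide variation (log-SD of amount per unit energy 0.5, as may hold for vitamins), power for a true 10% change is 0.21 on the absolute amount and 0.27 per unit energy, so little is gained.

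**Step 5: selective under-reporting.** Suppose one arm under-reports only fat, by 10%. Reported fat energy is 0.35 × 0.9 = 0.315 of true energy, reported total energy is 0.965, and the share is 0.315/0.965 = 32.6%, a false fall of 2.36 points. Then 2.36/0.866 = 2.72, giving 0.78. In simulation % of energy rejects falsely in 76-78% of trials and grams in 38-72%.

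**The case against.** A reader might infer that every nutrient outcome is an absolute amount, or that the trial would declare an improved profile merely because one arm ate or reported less. The documents support neither. Laboratory 25-hydroxyvitamin D and vitamin B6, food frequency and dietary habits are not daily amounts. No rule turns single nutrient tests into a verdict on the objective. A general fall would lower vitamin intakes as well as fat and salt, so it would not look favourable throughout, and it would show in total energy, which is analysed beside the nutrients.

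Further points have weight. Profile is undefined, and a set of daily amounts is a defensible reading; eating less fat or salt is a real dietary change. Both the control and intervention arms have dietitian contact (Protocol 5), so a 10% difference in reporting is supposed, not shown. Step 5 shows that energy scaling gives no protection when particular foods are under-reported, and can do worse than grams. The gain for highly variable vitamins is small. The calculations omit age, sex and the planned robust regression.

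This rules out replacing absolute amounts by energy-relative ones as the lead scale for all nutrients. It does not close the gap: total energy is listed but nothing ties it to the nutrient results, and none of the other measures describes macronutrient or salt composition.

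**Conclusion.** The point holds for the self-reported intakes. As planned, no single nutrient test separates a uniform difference in eating or reporting from a change in composition, and spread in energy weakens the tests for true macronutrient shifts. For fat the contrasts are about 39-73% against 5% under a uniform 10% fall, and about 22-40% against 81% power for a true 2.5-point shift. These figures are indicative only, because all intake SDs and correlations are assumed. The first contrast also assumes that under-reporting is the same across foods. The precision gain is supported for macronutrients and salt over most of the assumed range, and not for highly variable vitamins. This is one secondary objective of a pilot, so the change is worthwhile but not critical; the primary endpoint is untouched.

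**What to change.** In SAP 1.5 and 1.19, prespecify carbohydrate, fat, saturated fat and protein as % of energy, and salt per 1000 kcal, as outcomes for objective 2.2. Analyse each by ANCOVA on its own baseline value. Do not enter post-randomisation energy as a covariate; the ratio is the outcome. Report these side by side with the absolute amounts and total energy, and state that any conclusion about the nutrient profile rests on the energy-scaled results read together with energy. Vitamin intakes per 1000 kcal are optional.

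Name the instrument at the same time. SAP 1.19 treats the 24-hour recall and the food frequency questionnaire as one, at visits 4, 5, 7, 9 and 11. Protocol 3.4 and 6.2 keep them apart, with the questionnaire at the 6-, 12- and 26-week clinical visits and the follow-up recalls at the phone calls. Numerator and energy must come from the same record.

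The cost is SAP wording and a few derived variables from data already collected. There are two downsides: five more outcomes tested without multiplicity adjustment, and remaining bias if particular foods are under-reported, which should be stated as a limitation.
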